
of life. Beginning the management of clubfoot in early infants is technically less challenging due to childrens' rapid growth as well as easy tissue manipulation ^[15].

Reports on the failures of the Ponseti method have shown that the non-compliance with the bracing regimen following Ponseti casting is the primary reason for relapse ^[16]. Relapse or reoccurrence is defined as the reappearance of any of the components of the deformity including midfoot cavus, forefoot adductus, hindfoot varus and ankle equinus positioning of the foot ^[9,11]. A study done by Dobbs et al. 2004 showed that individuals who were non-compliant with their bracing were 183 times more likely to relapse. Previous literature reported that relapse rates between 10-30% are common^[17]. Of these relapses it is estimated that 78% of all relapses occur due to non-compliance with bracing, whereas only 7% of relapses occur with full compliance^[17]. Thus, it is critical that bracing regimens be followed strictly and consistently. One of the ways that this can be addressed is through improving brace design for comfort and long-term wear. Some of the most problematic causes for non-compliance with bracing are skin lesions such as blistering, sleeping problems from discomfort, parental concerns about the restrictiveness of leg movement in the brace, and dislodgment of the foot from the brace due to kicking ^[14,17,18]. In recent years the focus for the improvement of outcomes of CTEV following Ponseti casting has focused on the production of a brace that leads to higher compliance rates and therefore better treatment outcomes by addressing these four main problems with FAB. A few studies have reported increased compliance with reduced rates of relapse when adapting the bracing methodology via improving the standard rigid bar to be more dynamic ^[14,19]. In addition, Chen et al. 2007 created custom AFOs that they fastened to an articulating bar and found success in decreasing skin blistering (3.6% of patients in compared with 22% with traditional FAB) and non-compliance rates (7.2% compared to 42% with traditional FAB) as reported by parents. The AFO made by [name] was made of one-eighth-inch plastic copolymer physically molded to the patient's foot. A custom Duraflex liner was then inserted into the plastic molded piece and attached to an articulation bar. However, one drawback of their custom orthoses is that the average cost for the custom bracing was nearly 4 times that of the traditional brace ^[17]. Our orthoses would be more beneficial because it allows for the use and improvement of the already widely used Mitchell shoes, a much more cost-effective option. In addition, our orthoses are different in that the feet are scanned in 3D and edited in CAD before the inserts will be 3D printed. In general, most studies have focused on the feet are implementation of dynamic bars that allow greater range of motion ^[14,19]. The standard for the Ponseti brace is maintenance of the completely corrected foot in 60-70 degrees of external rotation on the affected side and in 30-40 degrees of external rotation on the normal side. The bar should be bent 5-10 degrees with the convexity pointing away from the child to hold the feet in a valgus position. The feet should be placed on the bar so that the heels of the shoes are at shoulder width ^[11]. Knees are left free so the child can kick straight and stretch the Achilles tendon. It is also important to note that compliance rates are almost always overestimated when being reported through parental survey and thus we will be assessing compliance rates using heat sensors inserted into the back of the insert orthotics in order to get a more accurate reading of time spent in the bracing apparatus ^[20]. The use of these sensors is new to research on bracing compliance for clubfoot and would be one of the first extremely reliable measures of parental compliance. Our custom orthotics should correct for the slipping of the infant's foot out of the Mitchell shoes as well as decreasing the number of skin lesions from rubbing on the leather shoe, thus increasing compliance and overall functional outcomes.

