The infant's feet will be scanned following removal of the second to last cast (allowing for orthotic production time and no extra visits) -from the middle of the tibia to the entire foot using Milwaukee Topographic system (located in the CHW Musculoskeletal Functional Assessment Center), which consists of handheld wand with two CCD cameras and one sensor to define trunk position in 3D space (Polhemus FastSCAN Scorpion, Colchester, VT). Only subjects receiving the custom orthotic insert will undergo scanning. The scanning procedure will take place after the final cast is removed and should take no longer than 5 minutes. The child will be placed into a supine position and the foot/feet will be passively manipulated to 60-70 degrees abduction and 10-15 degrees of dorsiflexion. The physician will hold the foot in place and a tech will scan the foot. Its geometry will be imported into the CAD software (Rodin4D, Paris, France) for designing the FO21. The scan will be uploaded to the epic system and a report will be generated. The report will then be sent to the Engineering team at the Orthotic Design Company, which is within the Milwaukee School of Engineering (MSOE), for manufacturing. The report will only contain raw topographic data and no identifying information. Patients will be assigned numbers to keep track of braces. The brace will be composed of biocompatible polyurethane (Elasto-75D). Following this the braces will be sent back and the patient will return to have the orthotic fitted by an orthoptist. This will likely take about a week and in the meantime all patients will wear the Mitchell shoes (Figure 1). A wireless temperature data logger (Orthotimer®) will be used to monitor brace wear for each patient (n = 10 sensors). The sensors featured a 3V battery and a data storage capacity allowing for the storage of temperature (precision of $\pm 0.1^{\circ}\text{C}$), date, and time every 15 minutes for 100 days. Batteries will not need to be changed since the minimum lifespan of the battery is 18 months. The sensors will be imbedded in the outside of the brace sandals, just above the heel, to avoid locations prone to skin irritation²². The sensor will be fused into the back of the Mitchell shoe and covered with a fabric flap that is sewn onto the shoe. The sensor and battery will not be removable and will not therefore pose a choking risk. Sensors will be calibrated upon fitting of the brace. The use of FO may cause skin redness, blisters, or rubbing. If these issues will be discovered during the regularly scheduled clinic visits, physicians will immediately request the orthotist to trim the orthosis or place additional foam on it. It must be addressed at the same time as the regularly scheduled clinic visits. It should be noted that the patient and their insurance company will be responsible for the cost of the standard Mitchell shoes and Ponseti bar, but will not be responsible for the costs of the FO, batteries, or sensor. All follow up appointments will coincide with normal clinical care except for a few additional processes during these visits (Table 1). At the end of the 6th month patients will be required to return the Orthotimer sensors but will be able to keep the custom orthotics. They should not need to get new orthotics because in the first 6 months of bracing, children often use the same shoes. We may assess the orthotic and have the orthoptist adjust the fit.

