
Table 1. Table of tasks to be performed at each clinical visit from the beginning of intervention to the end of the study period. Gray colored boxes indicate the task will be performed.

Task	Last Brace Removed	2 Week Follow Up	12 Week Follow Up	24 Week Follow Up
Check Foot				
Measure Dimeglio Score				
Scan Foot (Milwaukee Topographic System)				
Initial Survey				
Follow up Survey				
Transfer Data from Sensor				
Assess Fit and Adjust Orthotics as Needed				

Analysis of clubfoot functional outcomes will be assessed using Dimeglio Scores before and after Ponseti Casting as well as after 2, 12, and 24 weeks of bracing. Dimeglio scores are often used to assess the severity of clubfoot deformities and will give us a baseline as well as a level of improvement after casting and bracing. Dimeglio scores have been shown to provide good prognostic significance ^[5]. Other clinical parameters that we will be recording are: unilateral or bilateral CTEV, any surgeries performed (ex. achilles tenotomy, anterior tibial transfer, soft tissue release), level of brace adherence as reported by sensor, number of relapses, number of Ponseti casts needed to achieve correction, passive end dorsiflexion and abduction angles, and instances of rocker bottom deformity. The sensor to detect the body temperature will be embedded inside of the AFO and data will be stored in the sensors for three months. At follow up, the data will then be transferred to and saved to the computer via Bluetooth. In addition to these parameters we will use a parental questionnaire recording the following: occurrences of skin lesions, age of treatment initiation, age at each follow up, sex of child, prior treatments, family history of CTEV, parental marital status, insurance type, highest educational level achieved by parents, yearly family income, brace adherence as reported by parents, and reported of instances of foot slipping out of brace as well as any reasons for decreased compliance. Investigators will review the survey during clinical visits and will be able to address parent's concerns at that time. We are collecting data on these socioeconomic factors in order to help identify groups that may need additional attention or interventions in order to help reduce disparities in outcomes. Images of the child's feet in the orthotic or bracing device may be taken.

E. TOTAL NUMBER OF HUMAN RESEARCH PARTICIPANTS PROPOSED FOR THIS STUDY AT THIS SITE AND GLOBALLY. WHAT ARE THESE NUMBERS BASED ON?

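### Skin lesions, which the insert should reduce and may also cause, are study data only through the parental questionnaire; a standard clinician skin record in both arms is a cheap addition

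*Combined protocol and SAP*

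**What the plan says.** Section C (background) ties skin lesions to the rationale. It states: "Some of the most problematic causes for non-compliance with bracing are skin lesions such as blistering". It expects the insert to help partly by "decreasing the number of skin lesions from rubbing on the leather shoe", and so to raise compliance.

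Section D (design and methods) names the same problem as a risk: "The use of FO may cause skin redness, blisters, or rubbing". Section H repeats blisters as a risk of the custom orthosis. No other physical harm from the insert is named.

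The text after Table 1 in section D sets out what is collected. The clinical list begins "Other clinical parameters that we will be recording are: unilateral or bilateral CTEV, any surgeries performed" and ends "passive end dorsiflexion and abduction angles, and instances of rocker bottom deformity". Between these come sensor adherence, relapses and the number of casts. Skin is not on the list. It appears in the parents' part: "we will use a parental questionnaire recording the following: occurrences of skin lesions, age of treatment initiation". Investigators review the survey at clinic visits.

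On what clinicians see, section D says: "If these issues will be discovered during the regularly scheduled clinic visits, physicians will immediately request the orthotist to trim the orthosis". Adding foam is the stated alternative. Nothing is said about recording, grading or counting the finding. Table 1 has a row for checking the foot, with no stated content. Section D also allows, but does not require, images of the feet in the device.

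**The concern.** A lesion enters the data only if a parent remembers it and reports it. That parent knows whether the child has the insert, and the previous visit may be weeks past. A clinician examines the same foot at the same visit, yet the plan does not turn that examination into study data. The one described response to a skin finding, adjusting the orthosis, exists only in the insert arm.

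Two uses of the data are affected. The first is the safety record of a new device in infants, in a study that section M says has no safety monitoring board. The second is any lesion rate taken from this pilot into the larger study foreseen in sections E and O. Reporting error could run either way. Parents pleased with a custom device may report less, and parents whose child's insert is inspected and adjusted may report more.

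**Working it through.** The plan gives no event count, power or analysis for skin lesions, so there is no figure to reproduce. The check sets the provisions side by side and then gives a sense of scale.

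**1. Where skin findings go**

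| Source | Both arms? | Stated to be recorded as study data? |
|---|---|---|
| Parental questionnaire (section D) | Yes | Yes |
| Clinical parameter list (section D) | Yes | No skin item |
| Physician finding at a visit (section D) | Described for the orthosis only | Not stated; leads to adjustment |
| Check Foot row (Table 1) | Not stated | Content undefined |
| Images in the device (section D) | Not stated | Optional; not described as a skin assessment |

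**2. Length of recall**

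Inputs: assessments after 2, 12 and 24 weeks of bracing (section D and Table 1).

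- If the survey is given at every follow-up visit, the gaps are 2 − 0 = 2, 12 − 2 = 10 and 24 − 12 = 12 weeks. The longest is 12 weeks.
- If it is not given at week 12, the longest gap is 24 − 2 = 22 weeks.

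The shading that would settle this is not readable, and the questionnaire, with any recall period it defines, is not in the documents.

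**3. What unequal reporting could do (illustration only)**

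Assume a true lesion rate of 22% in both arms, the blistering rate that section C cites for traditional braces. Assume that control parents report every lesion and insert-arm parents report a fraction s. The false difference is 0.22 × (1 − s).

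- s = 0.9: 0.22 × 0.1 = 2.2 percentage points
- s = 0.7: 0.22 × 0.3 = 6.6 percentage points
- s = 0.5: 0.22 × 0.5 = 11 percentage points

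The documents give no value for s. If control parents were the ones to under-report, the sign would reverse.

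**4. What five children per arm can show**

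Take the cited 22% (traditional) and 3.6% (custom) as an assumption.

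- Expected children with a lesion: 5 × 0.22 = 1.1 and 5 × 0.036 = 0.18, a difference of 0.92.
- Chance of no lesion in either arm: 0.78⁵ × 0.964⁵ = 0.24.
- Power of a two-sided Fisher exact test at 0.05: 0.8%. The smallest significant splits are 4/5 v 0/5 and 5/5 v 1/5 (both p = 0.048).

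Whatever the source, the lesion data can only be described.

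**The case against.** The strongest reply is that no planned comparison is harmed. Skin lesions are not among the three purposes in section A or in the hypothesis in section B, section H defines no safety endpoint, and section O names no lesion analysis. That stands, and it limits the point to a secondary safety measurement.

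A second reply is that a clinician check does not remove the main weakness and could be worse if used alone. The clinician also sees the insert. An examination on a few visit days misses lesions that heal in between, and only parents are present then. Both parts stand, so the clinician record should supplement the parent report, not displace it.

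Three stronger readings are tempting, and the documents do not support them.

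- A reader might infer from step 4 that one misreported child removes or doubles the expected difference, and take this as evidence of recall bias. The same holds for any source with five children per arm, so it measures the sample size. The cited rates also come from a different device on an articulating bar, and the sentence giving them ends by attributing its figures to parents' reports.
- A reader might infer that the plan contradicts itself, since section C says "compliance rates are almost always overestimated when being reported through parental survey" and then relies on parents for lesions. That remark concerns parents' accounts of their own adherence. It does not show that they misreport visible blisters.
- A reader might infer that skin findings in controls go unrecorded. The passage on adjustment says nothing about controls, the survey covers both arms, and clinicians may write skin findings in the chart. The plan simply does not make them study data.

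**Conclusion.** The point holds as a gap in measurement. Skin lesions are both a target and the only named physical risk of the insert, yet the sole stated study source is the report of parents who can see the arm. Recall runs to 12 weeks if the survey is given at every follow-up visit, and longer if it is not. That parents are unmasked is inferred from the visible insert and from the absence of any masking provision.

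The size of any bias cannot be derived from the documents. The 2.2 to 11 point range rests wholly on an assumed 22% rate and assumed under-reporting of 10% to 50% in one arm. No result of the trial is shown to be invalid, and no test of lesions is planned or feasible with 10 children. This is a worthwhile low-cost improvement; the study does not depend on it.

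**What to change.** Add a skin item to the clinical parameters in section D: for each foot, redness, blister or open lesion, each present or absent, with site. The clinician completes it at every existing follow-up visit, on the same form in both arms, before the survey is reviewed and before any adjustment of the orthosis. State in section O that it is reported descriptively by arm, next to the parent-reported occurrences.

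Keep the parent question and have it ask for the date each lesion was noticed, if it does not already. Section D expects about a week in the plain shoe before the insert is fitted, so the date also shows which device a child in the insert arm was wearing. Confirm in Table 1 which visits include the survey and the foot check.

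The cost is a few form fields and a sentence or two of protocol text. No extra visit is needed, and the handling of skin problems does not change. Two limits remain: the assessor knows the arm, and lesions that heal between visits are still known only through parents.

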We will be aiming to have 10 individuals in our preliminary trial before we move on to trying this method with larger cohorts. These numbers will allow us to run a power analysis to determine the number of individuals needed for a follow up study to confirm or refute any results we have found.

F. DRUGS OR PROCEDURES (may attach activity table if available - lab draws, EKG, chest x-rah, surgery, genetics, survey)

The participants will be scanned from the tibia to the tip of the toes by the Milwaukee Topographic system which consists of a handheld wand and sensors as well as spinal metrics. There will be a parental survey as a part of the research design. Manipulation of the foot via a trained individual will occur in order to assess the functionality and degree of deformity of the infant foot as we cannot assess gait at this early stage.

G. RISK CATEGORY:

X (1) [**45 CFR 46.404**](#) - Research not involving greater than minimal risk to the children.

(2) [**45 CFR 46.405**](#) - Research involving greater than minimal risk but presenting the prospect of direct benefit to the individual child subjects involved in the research.

(3) [**45 CFR 46.406**](#) - Research involving greater than minimal risk and no prospect of direct benefit to the individual child subjects involved in the research, but likely to yield generalizable knowledge about the subject's disorder or condition.

(4) [**45 CFR 46.407**](#) - Research that the IRB believes does not meet the conditions of 45 CFR 46.404, 46.405, or 46.406, but finds that the research presents a reasonable opportunity to further the understanding, prevention, or alleviation of a serious problem affecting the health or welfare of children.

H. RISKS AND THE PRECAUTIONS WHICH WILL BE TAKEN TO MINIMIZE RISK EXPOSURE

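### The hand-examined foot outcomes have no masking, no named scorer and no fixed place in the visit, so knowledge of the arm can bias them; sensor wear time is not affected

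*Combined protocol and SAP*

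**What the plan says.** Section F describes the foot assessment: "Manipulation of the foot via a trained individual will occur in order to assess the functionality and degree of deformity of the infant foot". It gives no role for that individual.

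Section D, after Table 1, plans "Dimeglio Scores before and after Ponseti Casting as well as after 2, 12, and 24 weeks of bracing". It also lists "number of relapses, number of Ponseti casts needed to achieve correction, passive end dorsiflexion and abduction angles, and instances of rocker bottom deformity". Relapse is defined only in the background (section C), without a threshold: "Relapse or reoccurrence is defined as the reappearance of any of the components of the deformity".

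Several parts of section D bear on what a scorer could know:

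- On scanning: "Only subjects receiving the custom orthotic insert will undergo scanning", and "The physician will hold the foot in place and a tech will scan the foot".
- Physicians who find skin problems at a clinic visit ask the orthotist to adjust the orthosis then and there.
- On the parent questionnaire, which covers adherence, slipping and reasons for lower compliance: "Investigators will review the survey during clinical visits and will be able to address parent's concerns at that time".
- Table 1 lists the Dimeglio score, the surveys, the sensor transfer and the fit check as visit tasks.

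The documents nowhere mention blinding or masking, require a scorer independent of treatment, or set the order of tasks within a visit. Section B states the expected direction: better compliance and function, and fewer relapses, with the custom orthosis.

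**The concern.** A score read by hand from a manipulated foot involves judgement. If the scorer knows the arm, or has just heard that the brace slips or is not worn, the reading can drift towards what is expected, and nothing in the plan guards against this. With 5 children per arm a small drift matters. Bias also differs from noise in that a larger follow-up study does not average it away once it has entered the planning assumption. Sections E and O give the power analysis for that study as a purpose of the pilot. If that analysis uses a foot outcome, the bias passes into the next sample size.

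**Working it through.** **Step 1. What the text establishes.**

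| Question | Documents |
|---|---|
| Is the foot examined by hand? | Yes, for functionality and degree of deformity (section F). For the angles and relapse the method is not described; manual examination is the likely reading. |
| Who scores? | A trained person, role not given (section F). |
| Do treating physicians learn the arm? | Yes, through the scan, done in one arm only, and through orthosis adjustments (section D). |
| Is the scorer one of them? | Not stated. |
| Is the survey seen before scoring? | Not stated. Investigators review it during clinic visits (section D). |
| Is there an outcome free of the scorer's judgement? | Yes: wear time from the temperature logger (section D). |

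**Step 2. Illustration for a child-level test.** The plan has no figure to reproduce: no effect size, SD or power stands behind the 10 children. Taken from the documents: 5 v 5 (section D), Student's t-test, two-sided 0.05 (section O). Assumed: no true effect, a between-child SD of 1.5 to 3 Dimeglio points, and a systematic leaning of 1 or 2 points between arms.

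The false-positive rate is the chance that a noncentral t variable with 8 df exceeds t(0.975, 8) = 2.306 in absolute value, with noncentrality = leaning / (SD × √(2/5)). For a leaning of 1 and SD 2 this is 1 / (2 × 0.632) = 0.79.

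| Leaning | SD 1.5 | SD 2 | SD 3 |
|---|---|---|---|
| 1 point | 15.4% | 10.8% | 7.5% |
| 2 points | 45.8% | 28.6% | 15.4% |

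In SD units, leanings of 0.25, 0.5, 0.75 and 1.0 SD give 6.4%, 10.8%, 18.2% and 28.6%.

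**Step 3. The test actually planned.** Section O treats each foot of a bilateral case as independent. As an extreme case, suppose all children are bilateral (10 feet per arm). In simulation (40,000 runs), a between-feet correlation of 0.5 to 0.9 makes the foot-level test reject 11.9% to 18.3% of the time with no leaning, and 25.2% to 30.6% with a leaning of 0.5 SD. The leaning thus adds about 13.3 points (25.2 − 11.9) to 12.3 points (30.6 − 18.3) on top of the separate problem of counting feet as independent.

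**Step 4. Planning the follow-up study, if it is sized on a foot outcome.** With 5 v 5, 80% power needs a difference of about 2.02 SD, so the p-value matters less than the estimate carried forward. The normal-approximation formula is n per arm = 2(1.960 + 0.842)² / d² ≈ 15.7 / d². The true effects and leanings below are assumptions.

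| True effect | Leaning | d used | n per arm | Actual power |
|---|---|---|---|---|
| 0.5 SD | 0 | 0.5 | 63 | 80% |
| 0.5 SD | 0.25 SD | 0.75 | 28 | 46% |
| 0.5 SD | 0.5 SD | 1.0 | 16 | 29% |
| 0.8 SD | 0 | 0.8 | 25 | 81% |
| 0.8 SD | 0.25 SD | 1.05 | 15 | 59% |
| 0.8 SD | 0.5 SD | 1.3 | 10 | 43% |

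Actual power is Φ(d_true × √(n/2) − 1.960). For 28 per arm: 0.5 × √14 − 1.960 = −0.089, which gives 46%.

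**The case against.** The case against rests on how much is inferred from silence, and most of it stands as a limit on the claim.

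- A reader might infer that the scorer knows the arm and has read the survey. The documents do not say so. They show that treating physicians learn the arm and that investigators review the survey, but not that either is the scorer, nor which task comes first. The insert also sits inside the shoe, and every child's shoe carries a sensor. What remains is that nothing prevents the scorer from knowing.
- A reader might infer that every foot outcome is exposed. Surgeries performed are recorded events, and the number of casts precedes bracing. Sensor wear time, which serves the first listed aim in section A, does not depend on the scorer.
- A reader might infer that the follow-up study will be planned on a biased estimate. Sections E and O promise a power analysis but name no endpoint. If wear time is used, Step 4 does not apply.
- Table 1 lists the foot check and Dimeglio rows above most of the survey and fit rows. It is a task list and sets no sequence. Its shaded cells are not legible in the text available here, so which tasks fall at which visit could not be checked.
- Visit order cannot mask someone who already knows the arm from recruitment, scanning, fitting or an earlier visit. This is correct, and it is why the scorer rule and the record of masking are needed as well.

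**Conclusion.** The concern holds in limited form. The plan leaves the Dimeglio score, and probably the passive angles and relapse, open to assessor bias, because it neither identifies the scorer nor separates scoring from information about the arm and the brace. That omission is established by the text; that bias would in fact occur is not. The size is unknown. The false-positive rates of 7.5% to 15.4% for a 1-point leaning, and 15.4% to 45.8% for 2 points, rest wholly on an assumed SD and leaning and on a child-level test, whereas the plan tests feet. The more serious consequence, an undersized follow-up study, depends on that study being sized on a foot outcome. The gap is worth closing before enrolment because the change is small. It does not undermine the wear-time comparison.

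**What to change.** In section D and Table 1, set one visit order for both arms:

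1. Shoes and any inserts are removed and put out of sight of the scorer.
2. The Dimeglio score, passive end angles and relapse (yes/no) are recorded.
3. Only then are the survey, sensor data and orthosis fit reviewed, at the same visit as now planned.

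State who scores, and apply one scorer rule to all children. Where existing staff allow, the same trained individual, who takes no part in scanning or fitting for any child, should score everyone. Do not merely exclude, child by child, whoever held the foot for the scan or fitted the insert. Those tasks occur only in the custom arm, so such a rule would change the scorer in that arm alone, confound scorer with treatment, and could itself reveal the arm.

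At each visit, record whether the scorer knew the arm, and report the foot outcomes as unmasked where that is so. If no uninvolved scorer is available, the visit order still keeps that day's survey, sensor and fit information from the scoring, but the results should be described as unmasked.

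The cost is a change of protocol wording, one extra item on the visit form and a small scheduling constraint, with no added visit or procedure. Masking will sometimes fail through skin marks, parents' remarks or prior knowledge of the arm.
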